#### **5.5 Medical History**

There are two CRFs contributing medical history data.

- Prior Study – Medical History CRF: Medical history as recorded during prior studies 005, 007 and 015 will be automatically uploaded to the Prior Study – Medical History CRF and medical history recorded during the 008 study will be recopied from the 008 records by the site to the Prior Study – Medical History CRF.
- Medical History CRF: Medical History discovered since the last visit in the prior study that is considered clinically relevant by the Investigator as well as prior study AEs that, at the Investigator's discretion, are judged clinically relevant will be recorded on the Medical History CRF.

Verbatim terms on CRFs will be coded to preferred term (PT) and system organ class (SOC) using the Medical Dictionary for Regulatory Activities (MedDRA) (version 16.0). The coding process is described in the Data Management Plan.

The number and percentage of subjects with a given medical history will be summarized for both CRFs combined for each system organ class and preferred term. The verbatim and coded medical histories from both CRFs will also be included in a listing. Newly added medical history will be flagged.

## **5.6 Concomitant Medications**

There are two CRFs contributing concomitant medication data.

- **Prior Study - Concomitant Medications CRF:** Concomitant medications as recorded during prior studies 005, 007 and 015 will be automatically uploaded to the Prior Study – Concomitant Medications CRF. These mapped medications will be available to the investigator at Visit 1 to use as a resource for completing the Concomitant Medications CRF. Concomitant medications recorded during the 008 study will be recopied from the 008 records by the site to the Prior Study – Concomitant Medications CRF.
- **Concomitant Medications CRF:** During Visit 1, all medications that were ongoing at the end of the prior study will be recopied by the site to the Concomitant Medications CRF. At each visit, any changes to existing concomitant medications and any new concomitant medications will be reviewed and recorded in the Concomitant Medications CRF. The date of commencement, dose, and date of any change of dose of concomitant medications are to be recorded.

Verbatim terms on case report forms will be coded to Anatomical Therapeutic Chemical (ATC) classes and Generic Drug Names using the World Health Organization (WHO) dictionary (WHODDE B2, March 1, 2013 release). The coding process is described in the Data Management Plan.

Each of the below summaries will be presented for each of the following:

1. Concomitant medications that were ongoing on Day 1 of dosing (pre-existing) - source is the Concomitant Medications CRF.
2. Concomitant medications that started on or after Day 1 of dosing (study-emergent) - source is the Concomitant Medications CRF.
3. All concomitant medications, whether pre-existing or study-emergent (merge of ongoing medications from the Prior Study - Concomitant Medications CRF and medications that were ongoing on Day 1 of dosing and medications that started on or after Day 1 of dosing from the Concomitant Medications CRF).

Concomitant medications will be summarized by WHO ATC classification level 1 term, ATC level 3 term and Preferred Term (generic name) with frequency and percentage of subjects. At each level of subject summarization, a subject is counted once if he/she reported one or more medications at that level. Each summary will be ordered alphabetically by each level of ATC class and generic drug name within each level of ATC class.

Concomitant medications will be listed with these elements as well as the verbatim drug name. Pre-existing medications, new medications as of the start of this study and medications that are initiated after the last dose of study drug will be flagged.

Prior medications will also be listed (separately). Prior medications are defined as those medications that were either started or ongoing at the end of the prior study participation and were stopped prior to the 020 first dose date.

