Tabular summaries of demographics and baseline characteristics will be prepared based on data collected at the Baseline visit for the original study of participation and at baseline for the open-label extension study. Tabular summaries of concomitant medication use (ongoing at start of study and newly initiated) will be restricted to the open-label extension study. All data, including study eligibility, will be listed.

Concomitant medications and recently used medications (anti-dementia and psychiatric drugs used within the prior 3 months) will be coded using the most current version of the World Health Organization (WHO) drug dictionary. Tabulations will be prepared of all drugs used concomitantly (relative to the first dose of study drug in the open-label extension study) based on WHO Anatomical Therapeutic Classification (ATC) level 1 term, ATC level 3 term, and Preferred Term (generic name) with frequency and percentage of subjects using each concomitant medication. Concomitant medications are to be listed with these elements as well as the verbatim drug name.

9.5 **Study Drug Exposure**

Total duration of exposure and mean daily dose per subject over the treatment period in the open-label study will be summarized descriptively. The proportion of subjects with dose interruptions and/or dose reductions will be summarized descriptively.

9.6 **Safety Analysis**

The analysis of safety will include summaries of AEs, laboratory tests, vital signs, ECGs, and physical and neurological examinations (including serotonin toxicity assessments).

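### SAP 5.6: the merge rule for all concomitant medications has no Day 1 condition, so a drug stopped before the first 020 dose could be tabulated as concomitant

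*SAP*

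**What the plan says.** SAP Section 5.6 uses two forms. The Prior Study form holds the double-blind medication record, uploaded automatically for studies 005, 007 and 015 and copied by hand for 008. The 020 Concomitant Medications form is completed in the extension. The SAP states: "During Visit 1, all medications that were ongoing at the end of the prior study will be recopied by the site" to that second form. Later changes and new drugs are also entered there.

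Three summaries follow:

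- Class 1: "Concomitant medications that were ongoing on Day 1 of dosing (pre-existing) - source is the Concomitant Medications CRF".
- Class 2: "Concomitant medications that started on or after Day 1 of dosing (study-emergent) - source is the Concomitant Medications CRF".
- Class 3: "All concomitant medications, whether pre-existing or study-emergent". Its sources are a "merge of ongoing medications from the Prior Study - Concomitant Medications CRF and medications that were ongoing on Day 1 of dosing", together with drugs started on or after Day 1 from the 020 form.

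The same section defines prior medications as those "started or ongoing at the end of the prior study participation and were stopped prior to the 020 first dose date", and sends them to a separate listing. The shell for that listing (16.2.4.3.1) draws on both forms.

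Protocol Section 9.4 says: "Tabular summaries of concomitant medication use (ongoing at start of study and newly initiated) will be restricted to the open-label extension study". It also anchors concomitant use to the first open-label dose.

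**The concern.** Classes 1 and 2 between them already cover everything the class 3 label promises, and both use the 020 form alone. Class 3 then brings in a further source. Drugs ongoing on Day 1 are named as their own element in the same sentence, so ongoing on the Prior Study form most naturally means ongoing when the double-blind study ended. A drug stopped between that point and the first 020 dose would then be a prior medication in one output and a concomitant medication in another.

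The affected outputs are the overall co-medication tables, 14.1.6.3.1 for all subjects and 14.1.6.3.2 for those not using AChEIs or memantine. Protocol Sections 4.7.2 and 4.7.3 single out serotonergic drugs and CYP and P-gp substrates for attention. A table of co-medication should therefore count drugs taken alongside open-label LMTM, not drugs already stopped.

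**Working it through.** The plan gives no figure to reproduce and no arithmetic applies. The check applies the definitions to each possible medication history. The gap is the time from the end of the double-blind study to the first 020 dose.

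| Medication history | Class 1 | Class 2 | Prior medication | Class 3, read literally | Concomitant under Protocol 9.4 |
|---|---|---|---|---|---|
| A. Ongoing at end of prior study, stopped in the gap | no | no | yes | **yes** | **no** |
| B. Ongoing at end of prior study, still ongoing on Day 1 | yes | no | no | yes | yes |
| C. Started and stopped in the gap | no | no | probably (the wording is loose) | no | no |
| D. Started on or after Day 1 | no | yes | no | yes | yes |

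Only row A conflicts. Writing P for records ongoing at the end of the prior study:

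- Class 3 as written = class 1 ∪ class 2 ∪ P.
- P consists of row A and row B records.
- Row B records are already in class 1 once the site has recopied them.
- So the Prior Study source adds row A records, plus any row B drug that the site failed to recopy.

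**Could a program follow the text literally?** Yes. Changes to medications are recorded on the 020 form, so a stop in the gap would appear there. The SAP describes no field for end-dating the uploaded medication record. For adverse events, SAP Section 7.1 does give the site an editable extension-study end date on the uploaded form. An uploaded drug record could therefore still read as ongoing when the merge is run.

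**Does the SAP handle the parallel case differently?** Yes. The combined adverse event class in Section 7.1 carries a note limiting it to the pre-existing and study-emergent classes. The medication class has no such note.

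**Effect on counts.** Section 5.6 counts a subject once at each ATC or generic-name level. Row B duplicates therefore change nothing. A row A record changes a count only where the subject has no class 1 or class 2 drug at that level. For example, a subject who stopped an antidepressant in the gap and takes no other would be added at the generic-name level. The same subject might not be added at ATC level 1 if another drug in that class continues.

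**Who can be affected.** Protocol Section 4.1 and SAP Section 3 allow entry at the final double-blind visit or at any later time, and both documents require repeat baseline assessments after more than 42 days. Gaps are therefore foreseen, but neither document says how many subjects have one or how many drugs were stopped in it.

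**The case against.** The strongest reply is that the label governs. Class 3 is headed as pre-existing or study-emergent, the titles of both tables repeat this, and the footnote in the Table 14.1.6.1.1 shell, which is reused for both, defines pre-existing as ongoing on Day 1. On this view the parenthesis only names the forms to be merged, and ongoing means ongoing into 020. The combined adverse event class also names the Prior Study form as a source without anyone supposing that it admits resolved events.

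Much of this stands. The narrower meaning is very probably what was intended, and a reader who inferred that the SAP deliberately counts stopped drugs as concomitant would go beyond the text. But the label does not cancel the merge rule printed beneath it, and the adverse event class is safe because its limiting note says so.

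A second reply also stands in part. The Prior Study record can legitimately supply a drug still in use that the site omitted when recopying. A reader might infer that the added source should contribute nothing at all. That is too strong, although class 1 would miss the same drug, so a data query is the better remedy.

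A reader might also infer that every drug stopped in the gap is misclassified. Row C shows otherwise: a drug both started and stopped in the gap is not an ongoing record on the Prior Study form.

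**Conclusion.** The concern holds as a drafting inconsistency of minor importance. The class 3 merge rule omits a condition that its own label, the prior-medication definition, the table footnote and Protocol Section 9.4 all imply. Read literally, it could place drugs stopped before the first 020 dose in Tables 14.1.6.3.1 and 14.1.6.3.2. The concomitant medication listing may share the fault, because its shell refers back to Section 5.6 for sources.

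Counts in the combined tables could exceed those from classes 1 and 2 together. The documents do not support saying that they would, since that needs a subject with a gap, a drug stopped within it, and no other qualifying drug at the same level.

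Nor do they support a wider effect. The class 1 and class 2 tables use only the 020 form. The MMSE model in SAP Section 8.1 uses AChEI/memantine status from the prior study's randomization. The protocol's Version 3.0 change summary moves drug-interaction analyses to the Integrated Summary of Safety.

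The conclusion rests on two assumptions: that ongoing on the Prior Study form means ongoing at the end of that study, and that stops in the gap are recorded on the 020 form and not on the uploaded record.

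**What to change.** Add one sentence to SAP Section 5.6: class 3 is classes 1 and 2 combined and excludes prior medications, matching the limiting note in the adverse event section. Then choose one of two sourcing rules:

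1. Use the 020 form only, and raise a data query for any drug that appears to be still in use but was not recopied. This is the simpler program and corrects class 1 as well. Its small cost is that the uploaded record no longer acts as a backstop if the query is missed.
2. Keep the Prior Study source, but admit a record only if the drug was not stopped before the first 020 dose, as checked against the 020 form. This keeps the backstop at the cost of a record-matching step.

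Either way, the Prior Study form remains a source for the prior-medication listing, so drugs stopped in the gap stay visible. The source note for the concomitant medication listing should follow the same rule. No data collection changes.

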## **6. EXTENT OF EXPOSURE**

There are four sources of data for determining exposure:

- The date of the first dose is collected on the First Dose of Study Drug CRF.
- The Drug Accountability CRF provides a sequential record of dispensing and return of tablets (including kit ID dispensed and a comment field).
- The Dose Adjustment / Interruption Log CRF provide a record of the start and stop dates of each treatment interruption and dose change (including a comment field).
- The Study Exit Status CRF provides a record of the date of the last dose of study drug.

For each subject, the total duration of exposure, exposure accounting for interruptions, mean and modal daily doses (including a dose of 0 for days not dosed and dose adjustments when applicable), highest daily dose, cumulative dose and dosing compliance, will be summarized descriptively. Notations on the Drug Accountability Log CRF about missed doses are not accounted for programmatically; these will be included in the listing.

Total duration of exposure is defined as the difference between the last dose date and the first dose date, plus 1 day. The total exposure duration defined above includes any periods where the dose is interrupted. A second calculation of exposure duration that excludes dose interruptions will also be performed.

Mean daily dose is calculated as follows:

$$\frac{\sum_{i=1}^n \text{Dose}_i(\text{mg/day}) \times \text{Duration}(\text{days}) \text{ on Dose}_i}{\text{Total Duration (days)}}$$

The cumulative dose (i.e., the numerator in the above formula) will also be summarized.

Compliance rate over the entire treatment period is calculated using the following formula:

$$\frac{(\text{Total Tablets Dispensed} - \text{Total Tablets Returned})}{\sum_{i=1}^n \text{Duration of Dose}_i \times \text{Frequency}_i - \sum_{j=1}^m \text{Duration of Dose Interruption}_j \times \text{Frequency of Interrupted Dose}_j}$$

where

- Duration of Dose*i* is defined as the last dose date - the first dose date +1 for the *i*th dosing regimen administered.
- Duration of Dose Interruption*j* is defined as the date of dose restart/adjustment – the date of the dose interruption for the *j*th dose interruption.
- Frequency*i* is the number of tablets taken daily during the *i*th dosing regimen.
- Frequency of Interrupted Dose*j* is the number of tablets taken daily during the dosing regimen that was interrupted.

This analysis will be repeated for subjects who returned an adequate amount of packages to allow for a meaningful calculation.

The frequency and percentage of subjects in the following duration of exposure categories (based on total duration of exposure, inclusive of interruptions) will be presented according to target visit windows defined in Appendix A.

The cumulative number and percentage of subjects across the categories will also be summarized, as well as total subject years of exposure, defined as the sum of exposure in years, will also be presented.

All study drug administration and compliance data will be presented in listings, including chronological dates of administration, number of tablets dispensed and returned with corresponding package ID, treatment duration, mean and modal daily dose, compliance, and any associated comments.

An additional listing will provide a chronological record of study drug administration including the first dose and any subsequent dose increases, reductions, or interruptions, and any associated comments.

## **7. SAFETY ANALYSES**

### **7.1 Adverse Events**

There are two CRFs contributing adverse event data.

- **Prior Study – Adverse Events CRF:** All adverse events as recorded during prior studies 005, 007 and 015 will be automatically uploaded to the Prior Study – Adverse Events CRF and adverse events recorded during the 008 study will be recopied from the 008 records by the site to the Prior Study – Adverse Events CRF. The only field that can be modified by the site is the OLEX end date as applicable. Additionally there is a comment field where text can be entered by site.
- **Adverse Event CRF:** New adverse events or changes to an existing adverse event will be recorded on the Adverse Event CRF.

Adverse events will be coded to SOC and PT using MedDRA (version 16.0). The coding process is described in the Data Management Plan.

AEs are grouped as follows and source(s) of data identified:

1. **Prior AEs:** AEs that were ongoing at the end of the prior study but that resolved before Day 1 of dosing in 020 or that started and resolved during the gap between studies. The source would be both the Prior Study – Adverse Events CRF and the (020) Adverse Event CRF.
2. **Pre-existing AEs:** AEs that were ongoing on Day 1 of dosing in 020 - source is the Prior Study – Adverse Events CRF. The source would be both the Prior Study – Adverse Events CRF and the (020) Adverse Event CRF.

3. Study-emergent AEs: AEs that started on or after Day 1 of dosing in 020, excluding post-treatment AEs (defined in #5 below). The source would be the (020) Adverse Event CRF.
4. All AEs: Whether pre-existing or study-emergent (merge of AEs that were ongoing on Day 1 of dosing) excluding post-treatment AEs. Sources are the Prior Study – Adverse Events CRF and the (020) Adverse Event CRF (note, this is a merge of #2 and 3 above *only*).
5. Post-treatment AEs: The study-emergent AEs (3# above) that have an onset more than 14 days after the last dose of study drug or that worsen in intensity or treatment attribution following discontinuation more than 14 days after the last dose of study drug.

The tabular summaries will be provided for AEs, with the number and percentage of subjects reporting each type of event. If a subject reports the same preferred term more than once, it is counted only once within that category. Further, for a given tabulation, the preferred term will only be counted once at its worst severity and strongest relationship to treatment.

After missing date imputation, if the end date and start date of two or more AEs with the same Preferred Term are less than or equal to two days apart, then the AE will be considered to be the same event and will be counted as one event. If the end date is missing for the first AE or the start date for the sequential AE is before the end date for the first AE, then the AEs will be considered one event and will be counted once. In every other case, the events will be counted separately.

The following summaries will be provided for AE categories 2-4 above:

- An overall summary of AEs summarizing the number and percent of subjects, and the number of unique AEs, in the following categories: any AE, severe AE, AE related to study drug, serious AE, related serious AE (serious adverse reaction or SAR), AE with outcome of death, adverse events of special interest (AESIs), AE leading to dose reduction, AE leading to dose interruption, AE leading to withdrawal of study drug, and AE leading to dose reduction, dose interruption, or withdrawal of study drug.
- Number of subjects who experienced AEs and total number of unique AEs by MedDRA SOC and PT.
- Number of subjects who experienced AEs by MedDRA SOC, PT, and worst severity.

- Number of subjects who experienced AEs by MedDRA SOC, PT, and strongest relationship to study drug (Related/Not Related). Events reported as “Possibly Related,” or “Related” will be included in the Related category. Events reported as “Unlikely Related” or “Not Related” will be included in the Not Related category. At each level of subject summarization a subject is classified according to the strongest relationship, as determined by the investigator, if the subject reported one or more events. AEs with a missing relationship will be considered related for this summary.
- Number of subjects who experienced serious AEs (SAEs) and total number of unique serious AEs by MedDRA SOC and PT (and subsets for fatal and nonfatal SAEs as well as related SAEs (SARs), as described above).
- Number of subjects who experienced severe AEs and total number of unique severe AEs by MedDRA SOC and PT. AEs with missing severity will be considered severe for inclusion in this summary.
- Number of subjects who experienced AEs leading to change in dose and total number of unique AEs leading to change in dose (dose reduction, dose interruption, and study drug withdrawal, separately and combined) by MedDRA SOC and PT.
- Number of subjects who experienced unique protocol-specified AESIs and total number of unique protocol-specified AESIs by MedDRA SOC and PT.

The above summaries of AEs will also be presented for non-AChEI (acetylcholinesterase inhibitor)/Memantine users. Selected summaries of AEs will also be presented by diagnosis and prior study treatment. Depending on controlled study results, analyses of selected TauRx AE groupings may be undertaken.

A tabular summary of post-treatment adverse events (#5 above) by MedDRA SOC and PT will be provided.

The AE listing will include Prior AEs, All AEs, and Post-treatment AEs (#1, 4, and 5 above). Prior AEs, Pre-existing AEs and Post-treatment AEs will be flagged.

In addition, listings will also be provided for study-emergent or post-treatment SAEs (including subsets for fatal and non-fatal SAEs), study-emergent AEs leading to dose reduction, interruption or study drug withdrawal, and study-emergent or post-treatment AESIs. Post-treatment AEs will be flagged.

---

 Relationship is determined by the Investigator

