14.3.2.9.3.2	Severe Adverse Events (Pre-existing Adverse Events and Study-emergent Adverse Events) by System Organ Class and Preferred Term – Non-AChEI/Memantine Users (Safety Population)
14.3.2.10.1.1	Adverse Events Leading to Dose Reduction that were Ongoing On Day 1 of Dosing (Pre-existing Adverse Events) by System Organ Class and Preferred Term (Safety Population)
14.3.2.10.1.2	Adverse Events Leading to Dose Reduction that were Ongoing On Day 1 of Dosing (Pre-existing Adverse Events) by System Organ Class and Preferred Term – Non-AChEI/Memantine Users (Safety Population)

Table Number	Table Description
14.3.2.10.2.1	Adverse Events Leading to Dose Reduction that Started On or After Day 1 of Dosing (Study-emergent Adverse Events) by System Organ Class and Preferred Term (Safety Population)
14.3.2.10.2.2	Adverse Events Leading to Dose Reduction that Started On or After Day 1 of Dosing (Study-emergent Adverse Events) by System Organ Class and Preferred Term – Non-AChEI/Memantine Users (Safety Population)
14.3.2.10.3.1	Adverse Events Leading to Dose Reduction (Pre-existing Adverse Events and Study-emergent Adverse Events) by System Organ Class and Preferred Term (Safety Population)
14.3.2.10.3.2	Adverse Events Leading to Dose Reduction (Pre-existing Adverse Events and Study-emergent Adverse Events) by System Organ Class and Preferred Term – Non-AChEI/Memantine Users (Safety Population)
14.3.2.10.3.3	Adverse Events Leading to Dose Reduction (Pre-existing Adverse Events and Study-emergent Adverse Events) by Diagnosis, Prior Study Treatment, System Organ Class and Preferred Term (Safety Population)
14.3.2.11.1.1	Adverse Events Leading to Dose Interruption that were Ongoing On Day 1 of Dosing (Pre-existing Adverse Events) by System Organ Class and Preferred Term (Safety Population)
14.3.2.11.1.2	Adverse Events Leading to Dose Interruption that were Ongoing On Day 1 of Dosing (Pre-existing Adverse Events) by System Organ Class and Preferred Term – Non-AChEI/Memantine Users (Safety Population)
14.3.2.11.2.1	Adverse Events Leading to Dose Interruption that Started On or After Day 1 of Dosing (Study-emergent Adverse Events) by System Organ Class and Preferred Term (Safety Population)
14.3.2.11.2.2	Adverse Events Leading to Dose Interruption that Started On or After Day 1 of Dosing (Study-emergent Adverse Events) by System Organ Class and Preferred Term – Non-AChEI/Memantine Users (Safety Population)

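### Pre-existing and merged AE tables in SAP 7.1 can take relationship and dose action from double-blind records, and the tables by prior treatment have no study-emergent version

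*SAP*

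**What the plan says.** SAP 7.1 names two sources of adverse event data.

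- The Prior Study form: "All adverse events as recorded during prior studies 005, 007 and 015 will be automatically uploaded to the Prior Study – Adverse Events CRF". Records from 008 are recopied onto it by the site. On editing, the SAP states "The only field that can be modified by the site is the OLEX end date as applicable"; a comment field is also available.
- The 020 form: "New adverse events or changes to an existing adverse event will be recorded on the Adverse Event CRF".

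Three of the five AE groups matter here.

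- Category 2 (pre-existing) is defined as "AEs that were ongoing on Day 1 of dosing in 020 - source is the Prior Study – Adverse Events CRF". The next sentence names both forms as the source.
- Category 3 (study-emergent) covers events starting on or after Day 1: "The source would be the (020) Adverse Event CRF".
- Category 4 is the merge of categories 2 and 3.

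The order for tables reads "The following summaries will be provided for AE categories 2-4 above". The list under it includes related AEs, serious adverse reactions (SARs) and AEs leading to dose reduction, interruption or withdrawal. One resulting title in Appendix F (Table 14.3.2.10.1.1) is "Adverse Events Leading to Dose Reduction that were Ongoing On Day 1 of Dosing (Pre-existing Adverse Events) by System Organ Class and Preferred Term". Within a preferred term the strongest relationship is kept, and in the relationship summary a missing relationship counts as related.

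Protocol 9.6.1 treats events ongoing at unchanged intensity and relationship as pre-treatment events that are not summarized, with pre-study AEs shown separately. SAP Section 1 limits reported safety data to study-emergent information. SAP Section 9 names no departure from the protocol and defers any changes to the study report.

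**The concern.** Protocol 7.1 defines action taken with regard to study drug. For a mapped event, that drug is the one given in the double-blind trial. Under protocol 4.5 the investigator did not know the assignment until that trial's blind was broken. If the event is still open on Day 1, its relationship and dose action can enter 020 tables without anyone having judged them against open-label LMTM.

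Long-term tolerability is a primary objective, and these tables describe it most directly. The risk is greatest where results are split by prior arm: dose reductions or attributions that differed between double-blind arms could be read as differences on open-label treatment.

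**Working it through.** No stated figure bears on this point, so the check traces the data flow and counts the tables.

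**1. What a mapped record carries.** The SAP does not list the uploaded fields. Protocol 7.1 includes relationship and action taken among the items recorded for each AE, and the SAP says events are uploaded as recorded. The upload of both fields is therefore inferred. If relationship were not uploaded, the missing-counts-as-related rule would place these events among the related ones, so the by-relationship tables are affected either way.

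**2. Whether such events can reach Day 1.** They can. Protocol 6.2.1 and SAP 3.3 provide for subjects from 007 who enter on a reduced dose. Protocol 4.2 excludes only interruptions longer than 30 days that made the subject ineligible to continue. Subjects who withdrew from the double-blind study are ineligible (protocol 5.1), so mapped records should contribute least to the withdrawal tables.

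**3. What happens when an event has two records.** A change seen in 020 goes on the 020 form, while the mapped record stays as it was. Same-term records that overlap or lie within two days are counted as one event, but the SAP does not say which record then supplies relationship and action. Under the strongest-relationship rule, a mapped Related outranks a later 020 Not Related in category 4.

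**4. Tables in Appendix F that use relationship or action taken.**

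| Set (14.3.2.x) | Category 2 | Category 3 | Category 4 |
|---|---|---|---|
| 1, overall summary | 2 | 2 | 3 |
| 4, relationship | 2 | 2 | 2 |
| 8, SARs | 2 | 2 | 2 |
| 10, dose reduction | 2 | 2 | 3 |
| 11, interruption | 2 | 2 | 3 |
| 12, withdrawal | 2 | 2 | 3 |
| 13, any of the three | 2 | 2 | 3 |
| Total | 14 | 14 | 19 |

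- All sets: 14 + 14 + 19 = 47 tables, of which 14 + 19 = 33 can take values from mapped records.
- Without set 1: (14 − 2) + (19 − 3) = 12 + 16 = 28 exposed tables.
- Set 1 adds 2 + 3 = 5 overall summaries.

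**5. Tables by prior treatment.** Five of these report related or dose-change events: 14.3.2.1.3.3, 14.3.2.10.3.3, 14.3.2.11.3.3, 14.3.2.12.3.3 and 14.3.2.13.3.3. All five are category 4, and none has a category 3 counterpart.

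**6. Size.** For a given dose action, let p3 be the proportion of subjects with a qualifying category 3 event and m the proportion with a qualifying mapped event open on Day 1. Ignoring category 2 events that come from the 020 form, the category 4 proportion lies between max(p3, m) and p3 + m. Neither p3 nor m is given in the documents.

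**The case against.** The strongest reply is that clean tables already exist. Every affected set has a study-emergent version built from the 020 form alone, as does the overall summary. The category 2 and 4 titles say that pre-existing events are included, so nothing is hidden. This stands. A reader might infer that all 020 tolerability results are contaminated or mislabelled; the documents do not support that.

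Four further replies stand in part.

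- A reader might infer that a 020 dose change caused by a pre-existing event cannot be captured. It can, because changes go on the 020 form, which is also a category 2 source. What is missing is a rule for choosing between the two records.
- A reader might take it as fact that a double-blind dose cut will be counted. The mapping specification is not among the documents, so this remains an inference, though a natural one.
- A reader might infer that tables and listings cannot be reconciled. The text of SAP 7.1 limits one listing to "study-emergent AEs leading to dose reduction, interruption or study drug withdrawal", but the shell for Listing 16.2.7.3.1 carries prior and pre-existing flags. The full AE listing also flags pre-existing events and shows relationship and action. Text and shell disagree and need aligning.
- Exposure has natural limits. AD subjects have at least three weeks off treatment before entry (protocol Section 2), and events that resolve in that gap fall into a group with no summary table. Subjects from 007 who enter on a reduced dose stay on it, so that reduction is still in force. The SAP shells label every prior arm as LMTM, 8 to 250 mg/day, although the protocol speaks of placebo; calling the prior treatment simply a different drug would go too far.

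These replies do not reach the merged tables by prior treatment. There, disclosure in the title does not separate the two sources, and no clean version is planned.

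**Conclusion.** The point holds in limited form. As written, category 2 and category 4 summaries of related AEs, SARs and AEs leading to dose reduction or interruption can draw relationship and action taken from mapped records that the site cannot re-assess. Withdrawal is least exposed. The merged tables mix double-blind and 020 attributions. In the five tables by prior treatment, double-blind arm differences can appear as 020 results, contrary to protocol 9.6.1 and SAP Section 1.

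Up to 28 tables plus five overall summaries are exposed. This is a count of tables, not of events: the distortion of any percentage cannot be derived from the documents. The conclusion rests on relationship and action taken being among the uploaded fields. It is worth correcting before the tables are programmed, but it does not undermine the study-emergent results.

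**What to change.** In SAP 7.1:

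1. Derive related, SAR, dose-reduction, interruption and withdrawal status only from records on the 020 Adverse Event CRF. Include pre-existing events whose change is recorded there. Restricting the tables to category 3 would not be enough: it is defined by onset, whereas protocol 9.6.1 also counts pre-existing events that worsen on treatment as treatment-emergent.
2. Where a mapped and a 020 record are merged, let the 020 record supply relationship and action.
3. Present mapped events without a 020 record by SOC/PT and severity at entry only. Keep category 2 relationship and dose-change tables only for events with 020 CRF fields.
4. Build the five tables by prior treatment on the same 020-only basis.
5. Align the listing text in SAP 7.1 with the flags in the Listing 16.2.7.3.1 shell.

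The cost is SAP wording and a source condition in the programs. No new data are needed.
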